Cover Page

Official Title of the Study: Teleoperation Experimental Comparison With Able-bodied Subjects

Document Date: July 19, 2022

NCT Number: NCT05048394

COMIRB Protocol

COLORADO MULTIPLE INSTITUTIONAL
REVIEW BOARD
[name] [contact] [contact]

Protocol #: 14-0838

Project Title: Biomechatronics Development Lab Myoelectric Controller protocol

Principal Investigator: [name]

Version Date: 07/19/22

I. Hypotheses and Specific Aims: The purpose of this protocol is to provide guidelines for research and development of more intuitively controlled myoelectric prosthesis. Self-identified adult volunteers will be used for convenience sampling for the population served.

II. Background and Significance: Currently available multi-joint prostheses cannot be fully utilized because there are fewer control inputs than the number of joints that need to be controlled. Based on the work in the field of neuroscience, it has been shown that grasping is a 'low dimensional' task (i.e. – only 2-3 control inputs are necessary). We will develop control paradigms and upper limb prostheses components to control a multi-joint prosthetic hand using currently available clinical practices and investigate which dimensions are most important for prosthetic devices.

III. Preliminary

Studies/Progress Report:

IV. Research Methods

A. Outcome Measure(s):

Outcome measures include completion rate, time to completion and path efficiency metrics as well as position of the arm, wrist, and hand during these tasks.

Additional outcome measures may include time of use, types of actions performed, location information (GPS), and/or power consumption. These metrics help define the performance of the postural control paradigm for EMG control and design of advanced prosthetic hands.

B. Description of Population to be Enrolled:

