#### Evaluating the efficacy of the *Semi-Autonomous Myoelectric Control Algorithm*:

**Hypothesis 1 (primary):** We hypothesize that use of *Semi-Autonomous Myoelectric Control Algorithm* will improve dexterity relative to the standard-of-care prosthetic treatment. To validate this hypothesis, we will compare the two treatments (Treatment 1 vs. 2) during a single laboratory-based session using a task involving the transfer of a fragile object, recording the transfer success rate. We will use an Anderson-Darling test to check for normality. If the sample is normally distributed, we will use a two-sample Student's t-test to compare Treatment 1 and 2. If the sample is not normally distributed, we will use a Wilcoxon Rank Sum test to compare Treatment 1 and 2. If the hypothesis is correct, then we expect Treatment 1 (the *Semi-Autonomous Myoelectric Control Algorithm*) to show a significantly higher transfer success rate than Treatment 2.

**Hypothesis 2 (secondary):** We hypothesize that use of *Semi-Autonomous Myoelectric Control* will also provide improved assistance with prolonged gross motor movements. To validate this hypothesis, we will compare the two treatments (Treatment 1 vs. 2) during a single laboratory-based session using a task involving holding an object in the air for 2 minutes and recording the number of times the object is dropped. We will use an Anderson-Darling test to check for normality. If the sample is normally distributed, we will use a two-sample Student's t-test to compare Treatment 1 and 2. If the sample is not normally distributed, we will use a Wilcoxon Rank Sum test to compare Treatment 1 and 2. If the hypothesis is correct, then we expect Treatment 1 (the *Semi-Autonomous Myoelectric Control Algorithm*) to show a significantly fewer drops than Treatment 2.

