### Power Calculation

Power was calculated using the 'sampsizepwr' package in MATLAB (version 2018a). The primary outcome measure, transfer success rate of the fragile object, was used to inform the power calculation. We used an average success rate of  $59.2\% \pm 20.7\%$  from [1]. We selected a z-test for normally distributed data with a known standard deviation to derive the number of subjects necessary to detect a 20% difference in success with 80% power. The result of this calculation indicated that a sample size of 9 subjects will achieve a power greater than 80%.

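### Does the 2-minute hold task need a stated clock rule before its drop count can be compared between treatments?

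*SAP*

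**What the plan says.** The SAP, under *Evaluating the efficacy of the Semi-Autonomous Myoelectric Control Algorithm*, sets out Hypothesis 2 (secondary): the algorithm "will also provide improved assistance with prolonged gross motor movements". The test of it is "a task involving holding an object in the air for 2 minutes and recording the number of times the object is dropped". If the hypothesis is right, Treatment 1 is expected "to show a significantly fewer drops than Treatment 2".

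The counts go to a two-sample t-test if an Anderson-Darling test supports normality. Otherwise: "If the sample is not normally distributed, we will use a Wilcoxon Rank Sum test to compare Treatment 1 and 2". Neither test has a term for time spent holding.

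The protocol adds nothing on this task. Its section on outcome measures reads: "Outcome measures include completion rate, time to completion and path efficiency metrics as well as position of the arm, wrist, and hand during these tasks". Its *Study Design and Research Methods* section describes target hand postures and moving physical objects, but no timed hold and no drop count.

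The SAP's *Power Calculation* concerns the primary outcome only. No figure is given for the drop count.

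**The concern.** Because the endpoint is a number of drops, a subject who drops the object presumably takes it up again and carries on. What the clock does in between then matters. If it runs on, each drop uses up part of the 2 minutes, and no further drop can occur until the object is back in the hand. A controller that is slow to re-grasp would collect fewer drops at the same grip stability, and the planned tests would score that as benefit.

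The secondary comparison could then show a difference where stability is equal, or hide one where it differs. If nobody records held time, the analysis could not undo this afterwards.

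**Working it through.** **The plan's own figure.** The only computed figure in the SAP is the 9 subjects for the primary outcome. Inputs from *Power Calculation*: SD 20.7 points, difference 20 points, power 80%, z-test with known SD. Assumed, because not stated: two-sided 5% level.

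- n = ((1.960 + 0.842) × 20.7 / 20)² = 8.41, rounded up to 9.
- Power at n = 9: 20 / (20.7 / √9) = 2.899; 2.899 − 1.960 = 0.939; power 82.6%.

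The figure reproduces. It does not involve the drop count, so nothing below changes it.

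**How the count behaves.** The documents give no drop rate and no re-grasp time, so every input here is assumed. Let H be the mean holding time per grasp and R the re-grasp time, both in seconds.

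- Clock running on: expected drops ≈ 120 / (H + R).
- Clock paused while the object is out of the hand: expected drops = 120 / H, whatever R is.

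With the clock running and equal stability in both treatments:

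| Drops per minute held | H | R = 2 s | R = 4 s | R = 10 s |
|---|---|---|---|---|
| 0.5 | 120 s | 120/122 = 0.98 | 120/124 = 0.97 | 120/130 = 0.92 |
| 1.5 | 40 s | 120/42 = 2.86 | 120/44 = 2.73 | 120/50 = 2.40 |
| 3 | 20 s | 120/22 = 5.45 | 120/24 = 5.00 | 120/30 = 4.00 |
| 6 | 10 s | 120/12 = 10.0 | 120/14 = 8.57 | 120/20 = 6.00 |

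Simulation with exponential holding times and a fixed re-grasp time agrees closely (for example 5.46 and 4.05 drops at 3 per minute with R = 2 s and 10 s).

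**What the planned test would do.** The simulation used 20,000 trials with 9 independent scores per treatment, a two-sample t-test at two-sided 5% and equal stability. Percentage of trials significant:

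| Drops per minute held | 2 s v 4 s | 3 s v 5 s | 2 s v 10 s | 2 s v 10 s, drop rates varying between subjects (CV 50%) |
|---|---|---|---|---|
| 0.5 | 5.1 | 4.9 | 5.1 | 5.2 |
| 1.5 | 5.4 | 5.0 | 8.6 | 6.9 |
| 3 | 7.4 | 6.8 | 33.8 | 18.2 |
| 6 | 21 | 20 | 96.8 | 57.7 |

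With a paused clock, or with equal re-grasp times of 5 s in both treatments, the rate stays at about 5% throughout (4.6% to 5.3%).

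So the distortion needs both frequent drops and a large difference in re-grasp time. The 97% cell requires a drop every 10 s of holding, a five-fold re-grasp contrast, and the same drop rate in every subject.

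**What the wording allows.** In the SAP's description of the task, the 2 minutes qualifies the holding. At least four procedures fit it:

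1. Two minutes of time held, with the clock paused after a drop: no bias.
2. Two minutes elapsed, with the subject re-grasping: the case worked above.
3. The attempt ends at a drop: re-grasp time plays no part.
4. Staff put the object back in the hand: the gap need not depend on treatment.

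Only the second carries the problem, and only if re-grasp times differ by treatment.

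**The case for a change.** The strongest case for acting is that the rule costs a sentence or two and a stopwatch, while lost holding times cannot be recovered. The trial compares two control methods, and nothing in the documents ensures that they re-grasp equally fast. Nor do the documents show that drops will be rare. If stability truly differs two-fold (1.5 v 3 drops per minute held), the chance of a significant result for the more stable controller is 81% with a paused clock. With a running clock it is 75% at equal 5 s re-grasp times, and 37% if that controller re-grasps in 2 s and the other in 10 s. Operators using different clock rules would also produce counts that cannot be pooled.

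Part of this stands: the available text states no rule, and under a running clock the count does depend on re-grasp time. What does not stand is the step from there to a fault in the plan. Nothing in the text favours the running clock over two minutes of holding. The 2 s v 10 s contrast has no basis in the documents, and modest contrasts give far smaller effects. The SAP's stated aim is help with prolonged movement; it does not promise a pure measure of grip stability. One alternative, the proportion of the 120 s held, would itself mix stability with re-grasp speed, so it would not remove the complaint.

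**Conclusion.** No change to the plan follows. This is a gap in the description of a secondary task, of the kind that the people running the session fill when they set up the timer. The most literal fillings, holding for 2 minutes or ending the attempt at a drop, create no bias from re-grasp time.

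A distortion arises only if the clock runs on and re-grasp times differ by treatment. On assumed inputs it is then negligible to small for modest differences: about 5% to 7% of trials significant at equal stability, for up to 3 drops per minute held. It is material only when drops are frequent and the difference is large. Its direction and size in this trial cannot be known from the documents.

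The SAP text available begins at *Statistical Power and Design*; an earlier part was removed and may describe the task, so even the absence of a rule is not certain. The simulated percentages also rest on exponential holding times, fixed re-grasp times and 9 independent scores per treatment. The primary endpoint and the sample size of 9 are unaffected in every case.

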### Power Calculation

Power was calculated using the 'sampsizepwr' package in MATLAB (version 2018a). The primary outcome measure, transfer success rate of the fragile object, was used to inform the power calculation. We used an average success rate of  $59.2\% \pm 20.7\%$  from [1]. We selected a z-test for normally distributed data with a known standard deviation to derive the number of subjects necessary to detect a 20% difference in success with 80% power. The result of this calculation indicated that a sample size of 9 subjects will achieve a power greater than 80%.

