The subject population will consist of a convenient sample of adult volunteers, both able bodied and limb deficient. The subjects will have various ethnicity, age, and gender. An estimated total of 60 subjects will be enrolled. The subjects must be able to understand and follow directions in English, assessed by their ability to respond during the recruitment and consent process. Exclusion criteria include any subjects that are not able to understand the procedures or are taking blood thinners. Subjects will be recruited via flyers placed at the Anschutz or Auraria campuses, flyers emailed to organizations that work with our target population, or in-person at conferences and events to which we have been invited.

Because of the potentially long distances we will need to travel to meet with participants and the demands of work on other researchers we will not be able to have more than one researcher travel at a time. In order to ensure the safety of a single researcher traveling to a participant's location, we will enforce the following safety procedures:

When traveling to off-site locations, researchers only a licensed and insured driver in a well-maintained vehicle with appropriate equipment for conditions will drive. Driver has AAA membership which will be used in case of emergency. Experimentation will only take place during normal business hours when other research staff can be reached in case of unanticipated emergency.

We will keep a log in the lab describing where we are traveling and with whom we are meeting. We will only travel to participants with whom we have previous contact and have determined to be safe. Traveling researcher will keep a cell phone with them and check in with other researchers in the lab at least every 3 hours via cell phone to confirm that they are safe.

C. Study Design and Research Methods

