The experiments will take place at the Biomechatronics Development Laboratory in the Children's Hospital on Anschutz campus, the University of Boulder Campus, and/or during normal at-home use. The participant will come up to 3 times for up to 4 hour sessions. An optional at-home use period can take place for up to 6 months. During this session the participant will be asked to control a virtual hand (a 3D image of a hand on the computer screen) and/or a prosthesis by contracting the muscles in the forearm and to manipulate physical objects on the table. The only devices coming into contact with the participant will be standard of care myoelectric control and motion capture equipment including surface and intramuscular electromyographic (EMG) sensors. Other equipment to be used in the laboratory include a data glove (Cyberglove II by Cyberglove Systems, LLC), vibrating motors, reflective markers (OptoTrak, Northern Digital Inc), and electrogoniometers (Biometrics Goniometer, Motion Lab Systems, Inc.). During at-home use, subjects will use standard of care surface EMG sensors installed into a prosthetic socket. Standard of care procedures involving palpation of the subject's arm will be used to locate the best position on the arm for the surface and Intramuscular EMG and motion capture sensors. The EMG sensors measure muscle activation levels and send the information to the computer to enable the control of the virtual hand or prosthesis. The motion capture sensors and goniometers give us a measurement of the position of the arm. A training period will be followed by several tests to measure the intuitiveness and functionality of several versions of the controller. Different versions of the controller will be presented to the subject in a randomized order. The subject will be expected to try and acquire target hand postures displayed on the screen using this control interface. Subjects will likewise be given a training period to practice moving the physical objects.

Additionally, we may travel to the subject's preferred location (*e.g.* home or office) to conduct testing with surface EMG, motion capture, goniometers, or video. This will allow us to maximize recruitment and include subjects who live too far from the Anschutz campus to participate.

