## Statistical Power and Design

### Data Analysis

Functional measure and subjective measure data will be gathered and evaluated carefully by study team members without conflicts of interest to determine the distribution of all scores in the population studied and the variability of scores within and between the two study groups.

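### The SAP's power claim for 9 subjects comes from a one-sample z-test with known SD; the two-sample t-test it plans has about 49% power at 9 per treatment (two-sided 5%), or 62% one-sided

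*SAP*

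**What the plan says.** The Power Calculation section of the SAP takes a mean success rate of 59.2% with SD 20.7% from one published study. It aims to detect a 20% difference with 80% power. On method it says: "We selected a z-test for normally distributed data with a known standard deviation". On the result: "The result of this calculation indicated that a sample size of 9 subjects will achieve a power greater than 80" per cent. It ties this to the primary endpoint: "The primary outcome measure, transfer success rate of the fragile object, was used to inform the power calculation".

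For that endpoint, Hypothesis 1 specifies a different test. If the data pass a normality check, "we will use a two-sample Student's t-test to compare Treatment 1 and 2"; if they do not, "we will use a Wilcoxon Rank Sum test to compare Treatment 1 and 2".

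The available text states neither alpha nor sidedness, and does not say whether 9 is a total or a number per treatment. The design is also unsettled. The SAP's Data Analysis section mentions "variability of scores within and between the two study groups", which suggests parallel groups. The protocol (section C) says "Different versions of the controller will be presented to the subject in a randomized order", and Hypothesis 1 describes one laboratory session; both suggest that each subject uses both treatments.

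**The concern.** A one-sample z-test treats the comparator mean (59.2%) and the SD (20.7) as known constants, so the only sampling error is in one mean. The planned test estimates two means and the SD. For the same number per treatment, the variance of the estimated difference doubles, and the critical value comes from a t distribution. Power has to be lower.

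This is the only sample-size justification visible for the primary hypothesis. If it describes a test that will not be run, anyone judging whether the comparison is large enough is given too favourable a figure. A non-significant result could then be read as evidence of no benefit when the study had only an even chance of detecting the targeted difference.

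**Working it through.** **Inputs.** SD 20.7 and target power 80% are from the SAP's Power Calculation. The difference is read as 20 percentage points. The relative reading, 0.20 × 59.2 = 11.84 points, would need 24 by the same method, so it does not return 9. Alpha is assumed to be 5%. Results are two-sided, with one-sided in brackets.

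**1. Reproducing the plan's figure (one-sample z, known SD).**

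n = (z₀.₉₇₅ + z₀.₈₀)² × (SD/difference)² = (1.960 + 0.842)² × (20.7/20)² = 8.41, rounded up to 9.

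Power at n = 9: 20 × √9 / 20.7 = 2.899, and Φ(2.899 − 1.960) = 82.6%. At n = 8 it is 78.0%. One-sided 5% would give 6.62, rounded up to 7, so two-sided 5% is the assumption that returns 9.

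**2. The planned t-test, 9 per treatment.**

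Non-centrality = 20 / (20.7 × √(1/9 + 1/9)) = 20 / 9.758 = 2.05, on 16 degrees of freedom. The non-central t distribution gives 48.7% [62.4%].

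**3. Where the power goes, at n = 9.**

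| Test | Two-sided | One-sided |
|---|---|---|
| One-sample z, SD known | 82.6% | 89.5% |
| One-sample t, SD estimated | 71.9% | 84.1% |
| Two-sample z, 9 per treatment | 53.6% | 65.7% |
| Two-sample t, 9 per treatment | 48.7% | 62.4% |
| Rank-sum, 9 per treatment (simulated, normal scores) | 43% | 59% |
| Two-sample t, 9 in total, split 5/4 | 23.9% | 36.6% |

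**4. What 80% would take with the two-sample t-test.** Two-sided: 17 per treatment gives 78.0%, 18 gives 80.4%. One-sided: 13 gives 77.3%, 14 gives 80.1%. At 9 per treatment, the difference detectable with 80% power is 29.1 [25.4] points.

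**5. Unpaired t-test applied to 9 subjects who each use both treatments** (200,000 simulations). At correlations 0, 0.3, 0.5 and 0.7, power is 48.6%, 48.6%, 48.8% and 49.2% two-sided, and 62.5%, 64.4%, 66.8% and 70.0% one-sided.

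**6. Paired t-test on 9 subjects.** If 20.7 is the SD under each treatment, the SD of the difference is 20.7 × √(2(1 − ρ)).

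| ρ | SD of difference | Two-sided | One-sided |
|---|---|---|---|
| 0.3 | 24.5 | 57.6% | 72.3% |
| 0.5 | 20.7 | 71.9% | 84.1% |
| 0.7 | 16.0 | 90.4% | 96.1% |

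Power of 80% requires ρ of about 0.59 (SD of difference 18.7) two-sided, or about 0.44 (22.0) one-sided.

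**The case against.** The strongest defence is that the study is within-subject and the one-sample z-test stands in for a paired comparison. On that view the sizing is roughly right and the slip is the unpaired test named under Hypothesis 1. The randomized order of controllers and the single session support this, and the hypothesis is directional. With 20.7 as the SD of the difference, a one-sided paired t-test on 9 subjects reaches 84.1%.

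Part of this stands: under pairing, the claim of more than 80% is unsupported rather than shown false. But the SAP names neither a paired nor a one-sided test, and it presents 20.7 as the spread around an average success rate, not of a difference. Two-sided, the same paired test gives 71.9%.

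Four smaller points are fair:

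- The SAP's arithmetic is correct for the test it used; the fault is the mismatch with the analysis.
- A one-sided one-sample t-test also first passes 80% at 9 (79.1% at 8), but it is neither the stated z-test nor a two-sample test.
- One-sided power of the unpaired test does rise with within-subject correlation, but a simulation at 0.95 still gave only 78%.
- The rank-sum figures use normal scores, whereas that test is reserved for non-normal data, so they only illustrate.

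Nor does the protocol's enrolment figure help. "An estimated total of 60 subjects will be enrolled" refers to a general controller-development protocol covering able-bodied and limb-deficient volunteers, and is not tied to this comparison.

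**Conclusion.** The concern holds. The stated power belongs to a test that the SAP does not plan to run. For the t-test it does plan, a true 20-point difference would be detected about half the time at 9 per treatment, or 62% of the time if the test is one-sided on independent samples. Neither version reaches 80%, and nine per treatment is the reading generous to the plan.

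This rests on a 5% alpha, a difference in percentage points, and SD 20.7 under each treatment. The failure to reach 80% with the unpaired t-test does not depend on sidedness, or on whether subjects cross over for correlations up to 0.7. Only a change to a paired analysis could bring 9 subjects above 80%, and that depends on a quantity the SAP does not supply. The stated power needs correcting before it is relied on.

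**What to change.** State alpha, sidedness, whether 9 is per treatment or in total, whether each subject uses both treatments, and that 20% means percentage points if it does. Then replace the known-SD and power wording with one of the following.

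(a) If the two-sample test is kept: *With 9 per treatment, a difference of 20 percentage points, SD 20.7 and two-sided alpha 0.05, the t-test has 49% power.* A rank-sum figure of about 43% may be added if labelled as an illustration with normal scores.

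(b) If a paired t-test is adopted: *With 9 subjects each using both treatments, a difference of 20 percentage points and two-sided alpha 0.05, power is 72% if the SD of the within-subject difference is 20.7. If 20.7 is the SD under each treatment, power is 58%, 72% and 90% at correlations 0.3, 0.5 and 0.7.* A claim above 80% may stay only if the SAP states and justifies an SD of the difference of 18.7 or less.

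If one-sided 5% is intended, say so. The figures become 62% for (a) (59% rank-sum) and 84% for (b) at an SD of the difference of 20.7.

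The cost is confined to the SAP text, and no added subjects are required. Option (a) records a less favourable power and does not raise it. Option (b) changes the named primary test and needs a justified SD of the difference if the claim above 80% is to stay.
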